15.2.7. ANALYSIS OF SECONDARY EFFICACY VARIABLE FOR OPEN-LABEL PERIOD(S)

The observed values of the secondary efficacy measures at the OL baseline, and at each scheduled post-baseline open-label extension visit, will be summarized descriptively. Changes from open-label baseline in these measures will be summarized at each scheduled post-baseline open-label extension visit, based on both the DB and the OL baseline.

15.3. OTHER EFFICACY VARIABLES

15.3.1. OTHER EFFICACY VARIABLES & DERIVATIONS

15.3.1.1. Parkinson's Disease Sleep Scale (SCOPA) Nighttime Sleep (NS) / Daytime Sleepiness (DS)

SCOPA is a self-administered, validated short questionnaire that is used to assess NS problems (SCOPA-NS) and DS (SCOPA-DS) in subjects with Parkinson's disease.

The NS subscale addresses NS problems in the past month and includes 5 items with 4 response options ranging from 0 (not at all) to 3 (a lot). The maximum score of this subscale is 15, with higher scores reflecting more severe sleep problems. One additional question evaluates overall sleep quality

Document:

\

Author:

Version Number:
Version Date:Final 1.0
24FEB2020Template No: CS_TP_BS016 Revision 4
Effective Date: 01Apr2016

Reference: CS_WI_BS005

on a 7-point scale (ranging from slept very well to slept very badly). The score on this item is not included in the score of the NS scale but is used separately as a global measure of sleep quality.

The DS subscale evaluates DS in the past month and includes 6 items with 4 response options, ranging from 0 (never) to 3 (often). The maximum score is 18, with higher scores reflecting more severe sleepiness (Marinus-2003).

15.3.1.2. Unified Parkinson's disease Rating scale (UPDRS) parts II and III

The UPDRS is a scale used to follow the longitudinal course of Parkinson's disease. From the original scale, only parts II and III will be performed in this study.

For UPDRS Part II (Activities of Daily Living), 13 items will be recorded from 0 to 4. It will represent historical information from the past seven days as how the patient functioned in various activities of daily living. The maximum score is 52.

For the UPDRS Part III (Motor Examination), 25 items will be recorded from 0 to 4. It will represent an objective motor assessment at the time of evaluation. The maximum score is 100.

All items from both parts are scored on a 5-point scale (0 - 4) with higher scores indicating higher severity. Only subjects on-period data will be taken into account in this analysis (see Section 6.9).

15.3.1.3. Rapid Eye Movement (REM) Sleep Behavior Disorder Questionnaire (RBDQ)

The RBDQ is a 13-item patient self-rated questionnaire addressing the clinical manifestations of REM Sleep Behavior Disorder (RBD). Questions are brief and answered "yes" or "no", with a maximum total score of 13.

Items 1 - 4 assess the frequency and content of dreams and their relationship to nocturnal movements and other behavior. Item 5 inquires about self-injuries and injuries to the bed partner. Item 6 (including 4 subitems) assesses specific nocturnal motor behaviors, items 7 and 8 address nocturnal awakenings, item 9 assesses disturbed sleep in general and item 10 queries the presence of any neurological disorder (Stiasny-Kolster-2007, Cummings-2014).

15.3.1.4. Zarit Burden Interview (Zarit-22)

The Zarit Burden Interview was designed to reflect subjective burden of caregivers of impaired elderly patients. The caregiver is asked to complete a questionnaire of 22 questions about the impact of the patient's disability on their life. For the first 21 items the caregiver is to indicate on a 5-point scale (0 - 4) how often they felt that way (Never, Rarely, Sometimes, Quite Frequently, or Nearly Always). On the 22nd item the caregiver indicates their overall impression of burden (Not at All, A Little, Moderately, Quite a Bit, Extremely). Zarit-22 questionnaire was administered during versions 1 though 5 of the protocol and was removed from version 6 of the protocol.

15.3.2. MISSING DATA METHODS FOR OTHER EFFICACY VARIABLE(s)

For rating scales with more than one item, if any item score contributing to the total score or individual domain score is missing, then the total score or individual domain score will be set to missing. The change from baseline scores will also be set to missing accordingly.

Document: \

Author:

Version Number:

Final 1.0

Version Date:

24FEB2020

Template No: CS_TP_BS016 Revision 4
Effective Date: 01Apr2016

Reference: CS_WI_BS005

The ANCOVA analyses of the continuous other efficacy variables will utilize the change from baseline at the Week 6 LOCF endpoints.

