Informed consent and blood sample for pharmacogenomics (CYPP450 2D6)		X				
Blood sample for plasma SEP-363856 PKh		X				X
Urine drug screen ⁱ	X					X
Scale for Assessment of Positive Symptoms (SAPS-PD)		X	X	X	X	X
Neuropsychiatric Inventory (NPI)	X	X		X		X
Clinical Global Impression – Severity (CGI-S)		X		X		X
Mini Mental State Exam (MMSE)	X	X		X		X
Unified Parkinson's Disease Rating Scale Parts 2 and 3 (UPDRS II and III)		X	X	X	X	X

Table 2: Schedule of Assessments – Double Blind Period (Continued)

	Screen/ Washout	Double-blind Treatment				
Study Visit Number	Visit 1	Visit 3 ^a	Visit 4	Visit 5	Visit 6	Visit 7/ OL Baseline
Study Visit Weeka	-2	1	2	3	5	6
Study Visit Day	-14 to -1	1	8 (± 2 d)	15 (± 2 d)	29 (± 2 d)	43 (± 2 d)
Scales for Outcomes in Parkinson's Disease Sleep Scale – Daytime Sleepiness (SCOPA-DS)		X		X		X
Scales for Outcomes in Parkinson's Disease Sleep Scale – Nighttime Sleep Quality (SCOPA-NS)		X		X		X
Rapid Eye Movement (REM) Sleep Behavior Disorder Questionnaire (RBDQ)		X		X		X
Columbia Suicide Severity Rating Scale (C-SSRS) ^j	X	X	X	X	X	X
Pretreatment event and Adverse events (AE) monitoring	X	X	X	X	X	X

Note: Footnotes appear under Table 3

Table 3: Schedule of Assessments – Open-Label Period

			Open-Labo	el Treatment			
Study Visit Number	Visit 8	Visit 9	Visit 10	Visit 11	Visit 12	Visit 13/ EOT/ET	Visit 14 Follow-up
Study Visit Week ^a	Week 7	Week 8	Week 9	Week 10	Week 14	Week 18	
(Open-label Week)	(OL Wk 1)	(OL Wk 2)	(OL Wk 3)	(OL Wk 4)	(OL Wk 8)	(OL Wk 12)	7 days post
Study Visit Day	$Day 50 \pm 2$	Day 57 \pm 2	Day 64 ± 2	Day 71 ± 3	Day 99± 3	Day 127 ± 3	last dose
(OL Study Day)	(OL Day 8)	(OL Day 15)	(OL Day 22)	(OL Day 29)	(OL Day 57)	(OL Day 85)	(± 2 days)
Concomitant Medications review	X	X	X	X	X	X	X
Dispense Study Drug ^c	X	X	X	X	X		
Study Drug Accountability	X	X	X	X	X	X	
Telephone contacts ^d		ell as at Study W	eek 12 and Weel		er a dose adjustm etween Visit 11 ar 13) ^d		
Physical Examination and neurological examination				X		X	X
Vital Sign Measurements ^e	X	X	X	X	X	X	X
Weight ^l				X		X	X
12-Lead Electrocardiogram (ECG)				X		X	
Hematology, Chemistry, and Urinalysis				X		X	
Serum prolactin ^k				X		X	
Blood sample for plasma SEP-363856 PK ^h				X		X	
Serum or plasma glycosylated hemoglobin (HbA _{1c})				X		X	
Serum or plasma glucose and lipid panel				X		X	
Breath alcohol text				X		X	
Urine drug screen ⁱ				X		X	
Neuropsychiatric Inventory (NPI)	X ^m			X	X	X	
Scale for Assessment of Positive Symptoms (SAPS-PD)				X	X	X	

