5.4. Other Objectives

Double-blind Period:

- To evaluate the effects of SEP-363856 sleep quality as measured by the Scales for Outcomes in Parkinson's Disease for nighttime sleep quality (SCOPA-NS) and daytime sleepiness (SCOPA-DS).
- To evaluate the effects of SEP-363856 on motor symptoms associated with Parkinson's Disease as measured by the Unified Parkinson's Disease Rating Scale Parts 2 and 3 (UPDRS II and III).

To evaluate the effects of SEP-363856 on Rapid Eye Movement (REM) Sleep Behavioral Disorder (RBD) symptoms as measured by the RBD questionnaire (RBDQ).

Open Label Period:

- To further evaluate the effectiveness of flexibly-dosed SEP-363856 over 12-weeks of treatment using:
 - Neuropsychiatric Inventory (NPI)
 - Clinical Global Impression-Severity (CGI-S)
 - Mini Mental State Exam (MMSE)
 - SAPS-PD
- To evaluate the effects of SEP-363856 on sleep quality as measured by the Scales for Outcomes in Parkinson's disease for nighttime sleep quality (SCOPA-NS) and daytime sleepiness (SCOPA-DS).
- To evaluate the effects of SEP-363856 on motor symptoms associated with Parkinson's Disease as measured by the Unified Parkinson's Disease Rating Scale Parts 2 and 3 (UPDRS II and III).
- To evaluate the effects of SEP-363856 on Rapid Eye Movement (REM) Sleep Behavioral Disorder (RBD) symptoms as measured by RBD questionnaire (RBDQ).

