- Blood samples for clinical laboratory evaluation (hematology, serum chemistry, serum prolactin, HbA_{1c}, glucose panel, and lipid panel)
- Perform breath alcohol test
- If subject and caregiver signed separate genetic informed consent, collect blood samples for pharmacogenomics (CYPP450 2D6)
- Urine sample for urinalysis
- Blood sample for determination of plasma SEP-363856 and SEP-363854 (predose, and 1 sample between 1-3 hours post dose)
- SAPS-PD
- NPI
- CGI-S
- MMSE

- UPDRS II and UPDRS III
- SCOPA-DS
- SCOPA-NS
- RBDQ
- C-SSRS
- Adverse events
- Review randomization criteria
- Randomize to treatment
- Dispense study drug
- Administer first study drug dose

After receiving the initial dose, subjects will remain in the clinic for at least 2 hours of clinical observation, which will include periodic assessments of orthostatic vital signs (1 hour [\pm 15 min] and 2 hours [\pm 15 min] post dose); additional medical assessments can be performed as needed per investigator discretion. Findings will be collected on appropriate case report forms (CRFs). Subjects will be discharged home if medically stable. Telephone calls to the subjects will be made on the first 2 days following the visit (see Section 11.9.11).

If subject appears to be symptomatic as assessed by the site during a telephone contact and requires additional assessments in-clinic, an unscheduled visit will be made as early as possible (see Section 11.9.12).

11.9.3. Visit 4 (Day 8 ± 2 days), Visit 5 (Day 15 ± 2 days), and Visit 6 (Day 29 ± 2 days)

The following procedures will be conducted during each visit (unless otherwise specified):

- Prior/concomitant medications
- Study drug accountability
- Dispense study drug
- Vital sign measurements (including orthostatic effects)
- SAPS-PD
- NPI (Visit 5 only)
- CGI-S (Visit 5 only)
- MMSE (Visit 5 only)
- UPDRS II and UPDRS III
- SCOPA-DS (Visit 5 only)
- SCOPA-NS (Visit 5, only)
- RBDQ (Visit 5, only)

- C-SSRS
- Adverse events

If the subject titrates up, the subject will remain in the clinic for at least 2 hours of clinical observation, which will include periodic assessments of orthostatic vital signs (1 hour [\pm 15 min] and 2 hours [\pm 15 min] post dose); additional medical assessments can be performed as needed per investigator discretion.

Telephone calls to the subjects will be made on the first 2 days after a dose adjustment (increase or decrease) (see Section 11.9.11).

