15.3.5.3. Other Efficacy Endpoint Analysis

Data from SCOPA-NS, SCOPA-DS, and UPDRS II and III, will be analyzed similarly.

The total score and change from baseline will be summarized by timepoint for each treatment group. Change from baseline at Week 6 will be analyzed by an analysis of covariance (ANCOVA) model with treatment as a fixed effect, and baseline score as a covariate.

The absolute values of the other efficacy measures at both the DB baseline and OL baseline, and at each scheduled post-baseline extension visit, will be summarized descriptively. Changes from baseline in these measures will be summarized at each scheduled post-baseline extension visit, based on both the DB baseline and the OL baseline.

The absolute values of SAPS-PD score at both the DB baseline and OL baseline, and at each scheduled post-baseline extension visit, will be summarized descriptively. Changes from baseline in SAPS-PD score will be summarized at each scheduled post-baseline extension visit, based on both the DB baseline and the OL baseline.

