15.3.3. ANALYSIS OF OTHER EFFICACY VARIABLES

15.3.3.1. Analysis of change from baseline in SCOPA-NS and SCOPA-DS total score at Week 6

The SCOPA-NS and SCOPA-DS total score and change from baseline will be summarized by timepoint for each treatment group. For SCOPA-NS and SCOPA-DS, change from baseline at Week 6 will be analyzed by an ANCOVA with treatment as fixed effect and baseline SCOPA-NS (or SCOPA-DS) as covariate. The ANCOVA analysis will utilize the Week 6 LOCF endpoint, which is imputed the same way the imputation done for primary endpoint (see Section 6.3).

15.3.3.2. The Overall sleep quality will be described (categorical) at each timepoint by treatment group. Analysis of change from baseline in UPDRS II and III total score at Week 6

The UPDRS II and III total score and change from baseline will be summarized by timepoint for each treatment group. Change from baseline at Week 6 will be analyzed by an ANCOVA with treatment as fixed effect and baseline UPDRS II or III total score as covariate. The ANCOVA analysis will utilize the Week 6 LOCF endpoint, which is imputed the same way the imputation done for primary endpoint (see Section 6.3). Only subjects on-period data will be taken into account in this analysis (see Section 6.9).

15.3.3.3. Analysis of change from baseline in RBDQ total score at Week 6

The RBDQ total score and change from baseline will be summarized by timepoint for each treatment group. Change from baseline at Week 6 will be analyzed by an ANCOVA with treatment as fixed effect and baseline RBDQ total score as covariate. The ANCOVA analysis will utilize the Week 6 LOCF endpoint, which is imputed the same way the imputation done for primary endpoint (see Section 6.3).

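### UPDRS II and III have four post-baseline double-blind ratings, but their only test is an ANCOVA on Week 6 LOCF values; the plan's own MMRM would avoid a bias whose direction cannot be known in advance

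*SAP*

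**What the plan says.** The motor objective is in Protocol 5.4: "To evaluate the effects of SEP-363856 on motor symptoms associated with Parkinson's Disease as measured by the Unified Parkinson's Disease Rating Scale". It sits among the other objectives, not the primary, secondary or safety ones. Protocol Table 2 and the visit lists in 11.9.2 to 11.9.4 place UPDRS II and III at baseline and at Visits 4, 5, 6 and 7 (Days 8, 15, 29 and 43), the same double-blind schedule as SAPS-PD.

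For the test, Protocol 15.3.5.3 reads: "Change from baseline at Week 6 will be analyzed by an analysis of covariance", with treatment and baseline score in the model. LOCF is not mentioned there. Protocol 15.3.12 brings in LOCF only as support for SAPS-PD and CGI-S.

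The SAP adds LOCF. Section 15.3.2: "The ANCOVA analyses of the continuous other efficacy variables will utilize the change from baseline", taken to a Week 6 LOCF endpoint. Section 15.3.3.2, on UPDRS: "Change from baseline at Week 6 will be analyzed by an ANCOVA with treatment as fixed effect and baseline UPDRS II or III total score". The baseline score is the covariate. A further sentence there reads: "The ANCOVA analysis will utilize the Week 6 LOCF endpoint, which is imputed the same way the imputation done for primary endpoint", with a pointer to Section 6.3. Section 6.3 lists SAPS-PD, CGI-S, NPI, NPI (H+D) and MMSE as scores to be imputed; UPDRS, SCOPA and RBDQ are not on the list. Section 3.7 states that nothing has changed from the protocol.

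By contrast, SAPS-PD (SAP 15.1.3) and CGI-S, NPI and MMSE (15.2.3) are analysed by MMRM on observed data, although the last three have only two post-baseline double-blind ratings.

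**The concern.** Protocol 4.1 explains that treating psychosis in this disease can worsen motor function, and Protocol 7.3.2 says the drug has not been given to patients with PD or PDP before. UPDRS II and III therefore provide the first motor data in the target population. For a measure on which harm is the worry, substituting an earlier score for the Week 6 score can work in the drug's favour.

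A gradual effect is plausible because exposure rises during the double-blind period: the Day 8 rating comes at the end of the starting-dose week, and up-titration is possible through Visit 6. Whether an effect does build is not known.

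The plan already has a method that uses all four visits without substitution, and applies it to a scale on the same schedule. Using LOCF as the only test here is out of line with the plan's handling of its other continuous scales, and it is not declared.

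**Working it through.** **Inputs from the documents.** About 24 active and 12 placebo subjects; baseline predose on Day 1; ratings on Days 8, 15, 29 and 43, which is 7, 14, 28 and 42 days after baseline. The documents give no UPDRS standard deviation, effect size, power or dropout rate, so everything below on size is assumed.

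**The plan's own figures.** Its only power figures are for SAPS-PD. With a two-sided t-test at 0.05, 34 degrees of freedom and noncentrality d × √(24 × 12 / 36) = 2.828d, power at d = 0.8, 0.7, 0.6, 0.5 is 59.4%, 48.6%, 37.8%, 27.9%. The plan states 59%, 48%, 37%, 27%. These agree within one point but say nothing about UPDRS.

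**Bias formula.** Let a share p of the active arm have its last rating early, let k be the motor effect at that rating divided by the Week 6 effect, and let placebo show no trend. Then

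LOCF difference / true Week 6 difference = 1 + p(k − 1).

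If worsening is linear, k = (days since baseline at last rating) / 42.

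- Last rating at Day 15: k = 14/42, so the fraction lost is 28/42. With p = 17% (about 4 of 24): 0.17 × 28/42 = 11.3%. With p = 25% (6 of 24): 0.25 × 28/42 = 16.7%.
- Last ratings spread evenly over Visits 4 to 6: mean k = (7 + 14 + 28)/(3 × 42) = 0.389. With p = 10%, 20%, 30% the loss is 6.1%, 12.2%, 18.3%.
- Last rating at Visit 6 (14/42 lost) against Visit 4 (35/42 lost): 3.3% to 8.3%, 6.7% to 16.7% and 10.0% to 25.0% at the same three rates.

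If k exceeds 1, meaning the motor effect at the last rating is larger than it would be at Week 6, the sign reverses and LOCF overstates the difference.

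**Bias against precision.** A simulation (24 against 12, 4,000 runs per setting) assumed linear worsening to 0.8 SD at Week 6, and dropout after each of the first three ratings that became more likely the worse the score just observed. It compared the LOCF mean difference with a likelihood estimate equivalent to an unstructured repeated-measures model. It had no baseline covariate and no early-termination or unscheduled ratings. The last column is √(SD² + bias²); for the first row, LOCF gives √(0.361² + 0.058²) = 0.37.

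| Dropout, active / placebo | Between-visit correlation | LOCF mean (SD) | Repeated-measures mean (SD) | Total error, LOCF / repeated measures |
|---|---|---|---|---|
| 17% / 13% | 0.5 | 0.742 (0.361) | 0.802 (0.384) | 0.37 / 0.38 |
| 16% / 13% | 0.8 | 0.734 (0.356) | 0.803 (0.371) | 0.36 / 0.37 |
| 29% / 23% | 0.5 | 0.690 (0.370) | 0.806 (0.419) | 0.39 / 0.42 |
| 28% / 22% | 0.8 | 0.674 (0.355) | 0.802 (0.387) | 0.38 / 0.39 |
| 42% / 34% | 0.5 | 0.611 (0.358) | 0.796 (0.456) | 0.40 / 0.46 |
| 40% / 33% | 0.8 | 0.607 (0.358) | 0.798 (0.419) | 0.41 / 0.42 |

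Under these assumptions the repeated-measures estimate stays near 0.80, while LOCF falls to between 0.74 and 0.61. The standard error moves the other way: LOCF is the more precise in every row, and its total error is no larger.

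**Who is affected.** LOCF also reaches some completers. SAP 6.9 treats a rating made outside an on-period as missing, so a Week 6 rating lost in that way would be filled with an earlier one. An MMRM does not recover the lost rating, but it does not enter the earlier score as Week 6.

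**The case against.** Several stronger readings are tempting, and the documents do not support them.

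- *That the trial throws visit data away and simply freezes dropouts' scores.* SAP 15.3.3.2 summarises UPDRS by timepoint and arm. Subjects who stop early should have a termination visit that includes UPDRS (Protocol 13.2, 11.9.9), and that score is assigned to the next planned visit before LOCF (SAP 6.3, 6.4). Unscheduled visits for symptomatic subjects also rate UPDRS (Protocol 11.9.12) and feed LOCF. Only the test leaves the intermediate visits unused.
- *That LOCF is merely a sensitivity method everywhere else.* This is true of the continuous primary and secondary endpoints. SAPS-PD response, listed among the secondary variables, is itself based on the Week 6 LOCF endpoint (SAP 15.2.2).
- *That motor harm will be understated.* The direction depends on a time course and dropout pattern that nobody knows yet. If worsening is transient during titration, or if subjects leave at a score worse than their Week 6 score would have been, LOCF could overstate it.
- *That an MMRM would gain power.* The simulation shows the opposite for precision, and at 16–17% dropout the bias of 0.06 to 0.07 SD is small beside a standard error of about 0.36.

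It is also fair to say that little is decided here. UPDRS is an other endpoint with a nominal p-value (SAP 7.4) in a study sized for exploration, and motor deterioration is also picked up through neurological examination and adverse events (Protocol 11.4.5, 15.3.6.5). The MMRM would leave out unscheduled ratings, where acute worsening may be recorded.

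These points limit the size and certainty of the problem. They do not explain why the scale with four ratings has the weaker missing-data method, or why the added LOCF is undeclared.

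**Conclusion.** The point stands as a low-cost improvement, not as a flaw that threatens the trial. The facts are plain in the documents: four post-baseline ratings, a single test based on LOCF, a protocol that does not call for LOCF on this scale, and an SAP that reports no change.

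The size is conditional. With linear worsening, no trend on placebo and 10% to 30% active-arm dropout, LOCF understates the Week 6 motor difference by about 6% to 18% when last ratings are spread over Visits 4 to 6, and by 3% to 25% at the extremes of last visit. The Day 15 example gives 11% or 17%. With a different time course the sign could reverse. The MMRM removes this bias only if data are missing at random.

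A reader might infer that the trial's efficacy result is at risk, or that the plan hides motor harm. Neither follows: the primary analysis does not use this method, and the by-visit UPDRS tables will be reported.

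**What to change.** In SAP 15.3.3.2, analyse change from baseline in UPDRS II and in UPDRS III with the MMRM of 15.1.3: treatment, visit, treatment-by-visit interaction, baseline score, unstructured covariance with the convergence fallback already stated there, and Kenward-Roger degrees of freedom. Keep the Week 6 LOCF ANCOVA as a supportive analysis; it also retains the unscheduled ratings. Enter the change in SAP 3.7, and add to SAP 6.3 the scales to which LOCF applies. SCOPA-NS, SCOPA-DS and RBDQ could follow for consistency with CGI-S, NPI and MMSE; the case is weaker there, with two post-baseline ratings each, and Protocol 15.3.5.3 does not name RBDQ.

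Cost: the model code exists in SAP Appendix 3 and no new data are needed. In exchange the team accepts a somewhat larger standard error, an openly declared departure from the protocol's ANCOVA, and a main UPDRS analysis that does not use unscheduled ratings.

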15.3.3. ANALYSIS OF OTHER EFFICACY VARIABLES

15.3.3.1. Analysis of change from baseline in SCOPA-NS and SCOPA-DS total score at Week 6

The SCOPA-NS and SCOPA-DS total score and change from baseline will be summarized by timepoint for each treatment group. For SCOPA-NS and SCOPA-DS, change from baseline at Week 6 will be analyzed by an ANCOVA with treatment as fixed effect and baseline SCOPA-NS (or SCOPA-DS) as covariate. The ANCOVA analysis will utilize the Week 6 LOCF endpoint, which is imputed the same way the imputation done for primary endpoint (see Section 6.3).

15.3.3.2. The Overall sleep quality will be described (categorical) at each timepoint by treatment group. Analysis of change from baseline in UPDRS II and III total score at Week 6

The UPDRS II and III total score and change from baseline will be summarized by timepoint for each treatment group. Change from baseline at Week 6 will be analyzed by an ANCOVA with treatment as fixed effect and baseline UPDRS II or III total score as covariate. The ANCOVA analysis will utilize the Week 6 LOCF endpoint, which is imputed the same way the imputation done for primary endpoint (see Section 6.3). Only subjects on-period data will be taken into account in this analysis (see Section 6.9).

15.3.3.3. Analysis of change from baseline in RBDQ total score at Week 6

The RBDQ total score and change from baseline will be summarized by timepoint for each treatment group. Change from baseline at Week 6 will be analyzed by an ANCOVA with treatment as fixed effect and baseline RBDQ total score as covariate. The ANCOVA analysis will utilize the Week 6 LOCF endpoint, which is imputed the same way the imputation done for primary endpoint (see Section 6.3).

